8.3 PHARMACOKINETICS

Blood samples will be collected for the measurement of isatuximab concentration as described in the PK/ADA flowcharts ([Section 1.3](#)). The actual date and time of each sample will be recorded. Instructions for the collection and handling of PK samples will be provided by the Sponsor or Sponsor's designee in a separate laboratory manual. These samples will be tested by the Sponsor or Sponsor's designee. Pharmacokinetic samples may be used for additional testing of analytical method performance such as incurred sample reproducibility. These data will not be included in the study report but will be kept on file.

Descriptive statistics on C_{trough} , and C_{eoI} - Isa-IV+Pd arm for C_{eoI} only-) such as the mean, standard deviation, coefficient of variation, geometric mean, median, and range will be provided by treatment Arms (Isa-SC+Pd or Isa-IV+Pd) as well as C_{trough} ratio (SC/IV) over time.

For the co-primary endpoint observed C_{trough} at steady state, ie, C_{trough} corresponding to predose at C6D1, see [Section 9.2.2](#).

For the key secondary PK endpoint, observed CT4W, ie corresponding to predose at C2D1, see [Section 9.2.3.1](#).

In addition, isatuximab concentrations will be used for population PK analysis by non-linear mixed effects modeling. Data from other studies might be added for model development. The population PK analysis will involve an estimation of inter-individual PK variability, the determination of the population PK parameters estimates and possibly the quantitative evaluation of potential effect of participant characteristics on the main PK parameters. More

precisely the impact of body weight on exposure will be assessed for justification of the flat dosing across body weight. Empirical Bayesian estimation of individual exposure parameters such as C_{max} , C_{trough} , and area under the curve (AUC) will also be computed. Those individual exposure parameters will then be investigated as predictive factors for clinical outcomes including safety and efficacy endpoints, if possible. Additional details of the analysis plan and the results will be provided in separate documents.

8.4 SAFETY ASSESSMENTS

Planned time points for all safety assessments are provided in the SoA ([Section 1.3](#)). Participants will stay at the site between 1 and 4 hours after each administration in Cycle 1. For subsequent cycles, participant's surveillance will be left at the Investigator's judgement.

For the first at-home administration, the HCP administering the SC formulation of isatuximab will stay for 30 minutes to ensure safety of the administration.

8.4.1 Body weight and Physical examinations

Investigators should pay special attention to clinical signs related to previous serious illnesses.

Body weight (kg) for all the participants will be recorded in eCRF. Physical examination consists of an examination of major body systems including neurological, digestive, extramedullary myeloma localizations, respiratory, hepatomegaly, splenomegaly, and lymphadenopathy.

Only clinically relevant findings will be reported in the eCRF as AEs.

8.4.2 Vital signs

The following vitals will be measured at site: heart rate, body temperature, respiratory rate (RR), and blood pressure (BP).

Note: Vital signs are assessed pre-administration, one hour after start of first administration and, for the IV arm only, 30 minutes after the start of the subsequent infusions. On site, vital signs are to be assessed at end of infusion/injection up to Cycle 5, and as clinically indicated.

8.4.2.1 At-home administration

For at-home administration, the following vital signs will be measured systematically just before and at the end of SC injection:

- Heart rate.
- Systemic blood pressure.
- Body temperature.
- Pulse oximetry (SPO2).

Normal parameters are described in [Table 18](#). These are given as a guide but might be adapted by the investigator based on the clinical history and participant basal values.

In case of abnormal parameters, investigator should be called prior to D-15 injections and if deemed appropriate by the investigator, the participant should be transferred to the investigator site.

Table 18 - Normal values for at-home administration*

Vital sign	Normal range
Heart rate	[50-100] bpm.
Systolic blood pressure	≥90 mmHg (or no lower than 20mmHg below the participant normal value).
Diastolic blood pressure	≥50 mmHg.
Body temperature	Oral temperature <38°C (or equivalent with other measurement).
Pulse oximetry	SPO2 ≥95% or below the participant normal value in the context of prior chronic respiratory disease.

* Given as a guide, should be adapted to the participant medical history.

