- i **Pomalidomide/Dexamethasone administration data:** Participants will be asked to maintain a diary to record the doses of pomalidomide/dexamethasone (except those administered by the study nurse/Investigator).
- j **Patient Expectations Questionnaire (PEQ):** Patient Expectations Questionnaire (PEQ-BL) will be completed on Cycle 1/D1 by the participant at the site prior to discussing their health/disease status, and prior to study treatment administration or other study related procedures. The time estimated to complete this questionnaire is 5 minutes (Appendix 15, [Section 10.16](#)).
- k **Patient experience and satisfaction Questionnaire (PESQ) and Patient's assessment of treatment (PAT) Questionnaire:** Patient Experience and Satisfaction Questionnaire-Follow-Up (PESQ-FU) will be completed on Cycle 1/D8, D15, D22, Cycle 2/D1, D15, Cycle 3/D1, Cycle 4/D1 and on Day 15 from Cycle 5 onwards. The overall patient experience and satisfaction questionnaire-end of treatment (PESQ-EOT) and PAT will be completed at the EOT visit by the participant at the site prior to discussing their health/disease status, or other study-related procedures. The time estimated to complete this questionnaire is 5 to 10 minutes (Appendix 15, [Section 10.16](#)).
- l **Physical examination:** To be performed at screening, prior to study treatment administration on Day 1 of Cycle 1, and then on Day 1 of each subsequent cycle (a flexibility of a maximum of 24 hours before IMP administration is allowed), and at the EOT visit. Consists of examination of major body systems including neurological, digestive, extramedullary myeloma localizations, respiratory, hepatomegaly, splenomegaly, and lymphadenopathy.
- m **Weight:** Weight will be assessed for participants in both arms on screening, at each administration of Cycle 1 and 2, at D1 of subsequent cycles, and at EOT.
- n **Vital signs:** Heart rate, temperature, respiratory rate (or pulse oximetry for at-home administration), and blood pressure to be assessed pre-administration, one hour after start of first administration and, for the IV arm only, 30 minutes after the start of the subsequent infusions. On site, vital signs are to be assessed at end of infusion/injection up to Cycle 5, and as clinically indicated. If at-home administration, vital signs are to be taken systematically just before and at the end of injection.

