4.2 AT HOME ADMINISTRATION

Home administration may be possible where permitted by national and local regulations.

After the first 5 cycles, at home administration by an HCP may be proposed to the participants in the SC arm on D15 from Cycle 6 onwards. Visits at Day 1, on the other hand, from C6 onwards will always be outpatient visits at clinic. The Investigator is responsible for approving a participant's initiation with home injections and is still responsible for all study procedures and participant's safety even when delegating infusion responsibilities to the home care company during this clinical study.

The decision to propose at home administration on D15 will be based on the absence of IR at C4 and C5, the hematology test at Day 1 of each corresponding cycle and the Investigator's judgement. Participant willingness and ability to adhere to the requirements of home administration need to be taken into account before initiating it.

D15 at home administration will be preceded immediately prior administration by a questionnaire comprising heart rate, systemic blood pressure, pulse oximetry, oral temperature, and appearance of novel clinical symptoms ([Section 6.4.1](#), [Section 8.4.2.1](#)). At-home administration will require full completion of the questionnaire (filling of the questionnaire should be recorded) while participant should be addressed to investigator site if he or she does not meet all the criteria. Reason for non-administration at-home (including data from the questionnaire) should be recorded.

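### Table 18 words the SpO2 criterion for home dosing the wrong way round: in prior chronic respiratory disease, a reading below the participant's own normal value counts as normal

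*Protocol*

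**What the plan says.** Section 4.2 of the Protocol allows SC-arm participants to receive the Day 15 dose at home from Cycle 6 onwards. A health care professional gives it after completing a questionnaire that covers heart rate and blood pressure and also "pulse oximetry, oral temperature, and appearance of novel clinical symptoms". A participant who does not meet all the criteria is directed to the site.

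Section 8.4.2.1 supplies the reference values in Table 18, in a column of normal ranges. The pulse oximetry entry is "SPO2 ≥95% or below the participant normal value in the context of prior chronic respiratory disease". The systolic pressure entry, which also refers to the participant's own value, allows 90 mmHg or more, or a value "no lower than 20mmHg below the participant normal value".

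The action attached to the table is: "In case of abnormal parameters, investigator should be called prior to D-15 injections". Transfer to the site follows if the investigator thinks it appropriate.

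The section qualifies the table twice. The body text says "These are given as a guide but might be adapted by the investigator based on the clinical history and participant basal values". The table footnote says "Given as a guide, should be adapted to the participant medical history".

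**The concern.** A normal-range cell should list the readings that can pass without action. The second part of this cell lists readings under the participant's usual level, which are the ones that should lead to a call. It sets no floor, and no other part of the Protocol gives an SpO2 threshold to fall back on.

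The cell matters because it feeds a decision taken at the bedside, away from the site. Oximetry is also the only respiratory measurement in the home check: footnote n of the Schedule of Activities lists "respiratory rate (or pulse oximetry for at-home administration", so it takes the place of respiratory rate. If the row is applied as printed, a symptom-free fall in saturation in a participant with chronic lung disease is labelled normal and the pre-injection call is not prompted.

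**Working it through.** The Protocol gives no figure to reproduce. The check is to write out the logic of the row, compare it with its neighbour, and look for text elsewhere that would override it.

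**1. The row as printed.** Let s be the reading and b the usual value of a participant with prior chronic respiratory disease. The cell says: normal if s ≥ 95, or if s < b.

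**2. What that does.** The Protocol gives no usual values, so those below are assumptions.

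| Assumed usual value b | Normal as printed | Abnormal as printed |
|---|---|---|
| 88% | under 88%, or 95% and above | 88% to 94% |
| 92% | under 92%, or 95% and above | 92% to 94% |
| 94% | under 94%, or 95% and above | 94% |

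With b = 92%, a reading of 85% meets s < b and is normal. A reading of 92%, the participant's stable level, meets neither condition and is abnormal.

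**3. The row as it should read.** Let m be a tolerance in percentage points. Normal if s ≥ 95, or if s ≥ b − m. With b = 92% and m = 0, the lower limit is 92%: 92% is normal and 85% is abnormal. With m = 2 the limit is 92 − 2 = 90%, and 85% is still abnormal. With m = 4 the limit is 92 − 4 = 88%, and 85% is again abnormal. The printed and corrected rows disagree on the 85% reading at each of these tolerances.

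**4. The neighbouring row.** The systolic entry limits how far a value may fall below the participant's own level. The oximetry entry requires the value to be below that level and sets no limit. Both use the participant's normal value as reference, but only the systolic row is the right way round.

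**5. Other text on oximetry.** Oximetry also appears in the Schedule of Activities (vital signs row and footnote n) and in Section 4.2. These say that it is measured, and footnote n says when. None gives a threshold, so nothing overrides the cell.

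**6. Who is exposed.** Home dosing is optional, SC arm only, Day 15 only, from Cycle 6. It requires no infusion reaction in Cycles 4 and 5, and investigator approval. The second part of the row applies only in prior chronic respiratory disease. The co-primary trough sample is drawn before the Cycle 6 Day 1 dose, ahead of any home dose.

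**The case against.** The strongest reply is that this is a drafting slip with little practical reach, and most of that reply stands.

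- The values are a guide, and the footnote asks for adaptation to medical history, which covers exactly the participants in question. The printed wording decides only where no individual limit was set.
- The intended meaning is probably that a usual value under 95% is acceptable, and a trained professional would probably read it that way.
- Other safeguards exist. "The Investigator is responsible for approving a participant's initiation with home injections", new symptoms are checked separately, a professional gives every home dose and stays at least 30 minutes after the first, and exclusion criterion E 30 keeps out severe conditions that could impair participation.
- The questionnaire used at the bedside is not reproduced in the Protocol, so whether it repeats the wording is unknown.

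What does not stand is the step from there to leaving the cell alone. A guide is consulted when nothing more specific has been set, and there this one points the wrong way. The intended tolerance, if any, cannot be inferred from the text.

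A reader might infer something stronger: that the sponsor chose to accept desaturation, that participants will be dosed at home while hypoxic, or that the home safety check fails as a whole. The documents do not support this. The systolic row shows that the authors knew the right construction. Harm would need both a missing individual limit and a literal reading that clinical sense resists, and the other vital signs and the symptom check still operate.

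**Conclusion.** The point holds as a correction to one safety cell. In prior chronic respiratory disease, Table 18 classes a reading below the participant's normal value as normal with no lower limit, and leaves a stable usual value under 95% uncovered. As printed, it would not prompt the call to the investigator for an isolated desaturation.

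The practical risk is small. It is confined to SC-arm Day 15 home doses from Cycle 6, in participants with chronic respiratory disease and no individual limit, when the reading is the only warning sign. No frequency can be given, because the Protocol does not say how many participants have such disease or will dose at home. Efficacy and PK endpoints are unaffected.

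The conclusion about the wording rests only on the printed text. The usual values and tolerances in the illustration are assumptions and say nothing about how often the situation arises.

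**What to change.** Replace the pulse oximetry cell in Table 18 with: *SpO2 ≥95%; or, for a participant with prior chronic respiratory disease, no lower than the participant's normal value (or no more than an investigator-specified number of percentage points below it)*. Any tolerance should be stated as points below the usual value, because a margin is a difference and cannot itself serve as a floor.

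Make the same correction in the home-administration questionnaire if it repeats the wording. Section 4.2 needs no change.

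The cost is one table cell and possibly one questionnaire line, with no new measurement. Amendment 04 corrected typing errors in another safety table (Table 17) and was classed as non-substantial. This change could be handled in the same way.

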8.4.3 Electrocardiograms

A 12-lead electrocardiogram (ECG) will be obtained as outlined in the SoA ([Section 1.3](#)).

8.4.4 Clinical safety laboratory tests

- See Appendix 2 ([Section 10.2](#)) for the list of clinical laboratory tests to be performed and to the SoA ([Section 1.3](#)) for the timing and frequency.
- The Investigator must review the laboratory results, document this review, and record any clinically significant changes occurring during the study as an AE. The laboratory results must be retained with source documents. See Appendix 3 ([Section 10.3](#)) for abnormal laboratory results reporting. Abnormal laboratory findings associated with the underlying disease are not considered clinically significant, unless judged by the Investigator to be more severe than expected for the participant's condition.

8.4.5 Pregnancy testing

- Refer to [Section 5.1](#) Inclusion criteria for pregnancy testing criteria; the Investigator is responsible for review of medical history, menstrual history, and recent sexual activity to decrease the risk for inclusion of a female participant with an early undetected pregnancy.
- Pregnancy testing (urine or serum as required by local regulations) should be conducted weekly during Cycle 1, and then on D1 of each cycle from Cycle 2, ie monthly at intervals during intervention (at study visits and if needed, at home in between visits).
- Pregnancy testing (urine or serum as required by local regulations) must be conducted corresponding with the time frame for female participant contraception in [Section 5.1](#) Inclusion criteria.

- Additional serum or urine pregnancy tests may be performed, as determined necessary by the Investigator, or required by local regulation, to establish the absence of pregnancy at any time during the participant's participation in the study.
- Refer to [Section 10.4.3](#) for duration of pregnancy testing.

8.4.6 Suicidal ideation and behavior risk monitoring

Not applicable.

8.4.7 Assessment of local tolerability

Local tolerability at injection site after SC administration of isatuximab will be assessed during clinical stay using eCRF hourly (relative to the start of administration) for duration of 4 hours at Cycle 1/D1, 1 hour after the end of injection for the following Cycle 1 administrations and at end of injection from Cycle 2 onwards ([Section 1.3](#)). In case of at-home administration, for the first isatuximab injection performed at-home, an additional assessment should be performed 30 min after the end of the injection.

Table 19 - Summary of assessment timelines for local tolerability

On site administration	Cycle 1 Day 1: End of Injection (EoI), 1h, 2h, 3h, 4h Cycle 1 Day 8 & Cycle 1 Day 15: EoI, 1h Cycle 2 and subsequent cycles: EoI.
At-home administration	1st injection from Cycle 6: EoI, 30 min Rest of cycles: EoI.

Any swelling (unless it lasts longer than 24 hours) as a result of the injection of the isatuximab solution volume is not to be reported as an AE/ AESI.

8.4.8 Assessment of frailty

Frailty in multiple myeloma patient will be evaluated using functional assessments, at Cycle 1 Day 1. This will be done using the Katz index of independence in activities of daily living (ADL) ([32](#)) and the Lawton instrumental activities of daily living scale (IADL) ([33](#)).

8.5 PATIENTS REPORTED OUTCOMES

Patient-reported outcome (PRO) measures to be included are the European Organization for Research and Treatment of Cancer (EORTC) core quality of life questionnaire with 30 questions (QLQ-C30), the EORTC myeloma module with 20 items (QLQ-MY20), the EQ-5D-5L, the Health Resource Utilization and Productivity will be assessed using the HRUPQ, the Patient Expectations Questionnaire at baseline (PEQ-BL), the Patient Experience and Satisfaction Questionnaires during treatment Follow-Up and at the End Of Treatment (PESQ-FU and PESQ-EOT) and the PAT. All questionnaires are described in this section and presented in Appendix 16 ([Section 10.16](#)).

All questionnaires have been designed for self-completion. All PROs are in electronic form (electronic patient-reported outcomes [ePRO]) and will be completed by the patient (study participant) using either the study mobile phone provided or the patient's own device. Alternatively, a dedicated website could be proposed to collect PROs as a backup solution in case of unavailability of handheld devices. To minimize any bias, participants will fill out the ePROs before clinician assessments and discussion of their clinical condition, treatment plan, AEs, and any other related topics that could influence participant's perception and feelings prior to responding to the questions. Timing for each assessment is detailed in SoA section.

Since participants are to complete ePRO questionnaires on their own, there will be 20 minutes time allocated for training participants on ePRO technology at Cycle 1 Day 1 visit. Meanwhile, assistance will be provided if a participant needs longer time to learn or have training questions (eg, a refresher) during subsequent cycles. For the ePRO data it is mandatory that a key person (eg, research nurse) at each site is responsible for ePRO data collection, in order to optimize participant compliance and to ensure data completeness.

Compliance rates for completion will be generated based on number of assessments completed divided by number of assessments expected (per protocol). Reason for non-completion will be documented.

The planned statistical analysis of the PROs will be detailed in the SAP.

European Organization for Research and Treatment of Cancer core quality of life questionnaire (EORTC QLQ-C30)

The EORTC QLQ-C30 is a cancer-specific instrument that contains 30 items and provides a multi-dimensional assessment of HRQL (34, 35, 36). The validity and reliability of the EORTC QLQ-C30 has been established in various types of cancers (37). This instrument provides a comprehensive assessment of the principal HRQL dimensions identified as relevant by cancer patients (physical functioning, emotional functioning, cognitive functioning, role functioning, social functioning, global HRQL, impact of symptoms and of toxicities). The EORTC QLQ-C30 is one of the standard instruments used in oncology for the evaluation of new cancer therapies.

The QLQ-C30 is composed of both multi-item scales and single-item measures. These include 5 functional scales (physical, role, emotional, cognitive, and social functioning), 3 symptom scales (fatigue, nausea and vomiting, and pain), a Global Health Status (GHS)/quality of life scale, and 6 single items (dyspnea, insomnia, appetite loss, constipation, diarrhea, and financial scales). All of the scales and single-item measures range in score from 0 to 100. A higher score for a functional scale/GHS represents a higher/healthier level of functioning/HRQL, whereas a higher score for symptoms/items represents a higher level of symptomatology/problems.

The recall period for this instrument is 1 week.

European Organization for Research and Treatment of Cancer quality of life myeloma module (EORTC QLQ-MY20)

The EORTC QLC-MY20 is to be used in conjunction with the EORTC QLQ-C30 to assess symptoms and side effects due to the treatment or the disease which impact HRQL in participants with multiple myeloma (38, 39). This instrument contains 20 items in 4 independent subscales covering 2 functional domains (future perspective and body image) and 2 symptom scales (disease symptoms and side effects of treatment). Higher scores for disease symptoms and side effects of treatment indicate more symptoms and side effects and lower HRQL, whereas a high score for future perspective and body image represents better outcomes.

Both EORTC QLQ-C30 and EORTC QLQ-MY20 are reliable and valid measures of HRQL in cancer patients and the 2 instruments together (50 items) take approximately 15 minutes on average to complete. The instruments have been validated and used in many countries.

European Quality of Life Group measure with 5 dimensions and 5 levels per dimension (EQ-5D-5L)

The EQ-5D-5L is a standardized measure of health status that provides a simple, generic measure of health utility, and consists of 2 sections: descriptive and VAS. The descriptive system consists of 5 dimensions: mobility, self-care, usual activities, pain/discomfort, and anxiety/depression. Each dimension has 5 levels: no problems, slight problems, moderate problems, severe problems, and extreme problems. The VAS records the respondent's self-rated health on a 20 cm vertical, VAS with endpoints labelled 'the best health you can imagine' and 'the worst health you can imagine' anchored from 0 to 100 respectively. This information can be used as a quantitative measure of health as judged by the individual respondents.

The EQ-5D-5L is designed for self-completion by participants. Response options are measured with a 5-point Likert scale with higher scores indicate better HRQL.

Health Resource Utilization and Productivity Questionnaire (HRUPQ)

Medical resource utilization and participant productivity will be collected from participants through the specific HRUPQ questionnaire developed for this study (initially adapted to early Phase TCD15484 and modified for EFC15951). The data collected include number, nature (emergency or routine) and duration of hospitalizations, emergency room visits and outpatient medical encounters and employment history. The HRUPQ contains 46 items and takes approximately 10-15 minutes to complete.

Patient expectation, experience and satisfaction questionnaires

Patient Expectations Questionnaire (PEQ-BL)

The PEQ-BL will be completed at baseline prior to study treatment administration or other study related procedures. This questionnaire has been designed to assess the expectations of the participants regarding both the treatment (side effects, worth taking) and the administration method (confidence, comfortability, pain, side effects, potential time-savings), as well as to

understand previous treatment experience from the participant (experience with injection methods for oncology medication). This questionnaire has been developed by Sanofi as internal measure and has been debriefed and adapted based on qualitative interviews with oncology participants.

This questionnaire contains 7 items and take approximately 5 minutes to complete.

Patient experience and satisfaction questionnaires (PESQ; PESQ-FU and PESQ-EOT)

The PESQ-FU has been designed to follow up on participant experience and satisfaction regarding the treatment (side effects, worth taking and overall satisfaction) and the administration method (confidence, comfortability, pain, side effects, potential time-savings and overall satisfaction). This questionnaire has been developed by Sanofi as internal measure and has been debriefed and adapted based on qualitative interviews with oncology participants. The PESQ-FU contains 9 items and take approximately 5 minutes to complete.

The PESQ-EOT has been designed to assess participant experience and satisfaction regarding the treatment (side effects, worth taking and overall satisfaction) and the administration method (confidence, comfortability, pain, side effects, potential time-savings and overall satisfaction). This questionnaire includes also additional items to assess participant preference on injection method (SC or IV) and location of administration (at home or at clinic). This questionnaire has been developed by Sanofi as internal measure and has been debriefed and adapted based on qualitative interviews with oncology participants. The PESQ-EOT contains 17 items and take approximately 5-10 minutes to complete.

Patient's Assessment of Treatment questionnaire (PAT)

In order to demonstrate from participant perspective that the overall benefits outweigh the disadvantages in the target patient population, Sanofi has developed an internal measure; the Patient Assessment of Treatment questionnaire (PAT). The PAT provides patient insights on the benefits and disadvantages of treatment, including an overall B/D ratio using a final question that provides a quantitative assessment of the patient's perceived B/D. The 4-item PAT is an internally developed non-disease specific and self-administered assessment. The PAT is a modification from the Sanofi developed Patients' Qualitative Assessment of Treatment (PQAT; initially developed for diabetes [\(40\)](#)) and has been debriefed with oncology patients during qualitative interviews. This questionnaire contains 4 items and take approximately 2-3 minutes to complete.

Timing of Assessments

Cycle 1 Day 1 will serve as the baseline assessment for all participants. While on treatment, ePROs are to be completed prior to treatment on Day 1 of every cycle, and at the EOT visit. The time estimated to complete the EORTC QLQ-C30 and the EORTC QLQ-MY20 together is approximately 10 to 15 minutes. The time estimated to complete the EQ-5D-5L is approximately 5 to 10 minutes.

Since the participants are to complete ePRO questionnaires on their own, there will be 20 minutes time allocated for training participants on ePRO technology at Cycle 1 Day 1 visit. Meanwhile, assistance will be provided if a participant needs longer time to learn or have training questions (eg, a refresher) during consequent cycles. For the ePRO data it is mandatory that a key person (eg, research nurse) at each center be responsible for ePRO data collection, in order to optimize compliance of the participant and to ensure completeness of the data. The planned statistical analysis of the 3 ePROs will be detailed in the SAP.

